10.6.2. Study Populations

10.6.2.1. Safety Population

The Safety Population consists of all patients who started therapy with randomized study medication.

10.6.2.2. Full Analysis Set (FAS) Population

The Full Analysis Set (FAS) Population consists of all patients who were treated more than 4 weeks with randomized study medication and had at least one postbaseline value of the primary endpoints.

10.6.2.3. Per-Protocol Population

The Per-Protocol Population, a subset of the FAS Population, is defined as all patients who completed the maintenance phase without any major protocol violations. The precise reasons for excluding patients from the Per-Protocol Population will be fully defined and documented before unblinding.

10.6.3. Demographics and Clinical History Data

Demographic variables and other baseline characteristics will be summarized by treatment group for the FAS Populations. Summaries of categorical variables (nominal or ordinal) will include frequency and percentage of patients at each level of response.

For continuous variables, the number of observations, mean, median, standard deviation, minimum, and maximum will be presented.

Treatment difference will be analyzed using two sample t-test or Wilcoxon rank-sum test for continuous parameters, and using χ^2 -test or Fisher's exact test for categorical parameters.

10.6.4. Efficacy Assessment

10.6.4.1. Primary Efficacy Variable

Maintenance Phase

From the statistical point of view, the question of therapeutic equivalence will be approached by calculating the upper limit and the lower limit of 95% one-sided confidence interval of the difference between both treatment groups of the primary endpoints:

- mean change in hemoglobin level between the baseline period and the evaluation period
- mean change in weekly dosage per kg body weight between the baseline period and the evaluation period

* The baseline period is the last four weeks of titration phase and the evaluation period is the last four weeks of maintenance phase. Hemoglobin, hematocrit and the dosage of epoetin for the baseline period will be collected at Week -4, Week -2 and Week 0, and those for the evaluation period will be collected at Week 24, Week 26 and Week 28.

To demonstrate the therapeutic equivalence, two one-sided test (TOST) procedures will be used. It decomposes the interval hypothesis into two one-sided parts – $H_0: d < d_L$ and $H_1: d > d_U$, where d is the difference of the mean change in each primary endpoint, d_L is the lower limit of 95% one-sided confidence interval and d_U is the upper limit of 95% one-sided confidence interval. Both of these one-sided intervals will be compared with the pre-defined clinical acceptance ranges for the corresponding parameters (± 0.5 g/dl for hemoglobin and ± 45 IU/kg/week for epoetin dosage, based on the respective reference means). The intervals will be calculated by means of ANCOVA model including treatment group as a factor and study center and baseline value as covariates.

The statistical evaluation of the primary endpoint “mean change in weekly dosage per kg body weight between the baseline period and the evaluation period” will be performed based on the nominal dosage declared on the labels of the pre-filled syringes.

As the dosage of epoetin and the corresponding level of hemoglobin are closely interrelated, a hierarchic test strategy will be used in the present trial. The test on a higher level of hierarchy can only be performed, should the target of the previous level be fulfilled. The overall equivalence statement is consistent with a positive outcome on both levels of hierarchy. Due to this reason, no adjustment of alpha values will be required on the separate levels. The levels of hierarchy will be defined as follows:

Level 1: Calculation of the upper limit and the lower limit of 95% one-sided confidence interval of the difference (test - reference) of the mean change in hemoglobin level between the baseline period and the evaluation period and comparison with the pre-defined acceptance range.

Level 2: Calculation of the upper limit and the lower limit of 95% one-sided confidence interval of the difference (test - reference) of the mean change in weekly dosage per kg body weight between the baseline period and the evaluation period and comparison with the pre-defined acceptance range.

Open-label Extension Phase

The statistical analysis of the results of the open follow-up extension period will be only descriptive. Depending on their distribution the target parameters will be presented with their mean, median, standard deviation and quartiles or with their incidences.

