6. INVESTIGATORS AND STUDY ADMINISTRATIVE STRUCTURE

This study will be performed at approximately 20 study centers located in Korea and Malaysia. At each study center, the PI will be responsible for ensuring that the investigation is conducted according to the signed Investigator agreement, the protocol, and good clinical practice guidelines.

The PI at each study center will be responsible for the management of the study, which will consist of maintaining the study file and the patient records, corresponding with the IRB, and completing the electronic case report forms (eCRFs).

List of study personnel and contract details, please refer to Appendix IV.

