8. STUDY OBJECTIVES

1. The primary objective is to demonstrate the therapeutic equivalence of PDA10 to Eprex[®] in patients with end stage renal failure (ESRD) on chronic hemodialysis.

The therapeutic equivalence shall be evaluated by the difference between treatment groups in the change in hemoglobin from baseline, while taking into account differences in epoetin dosage.

2. The secondary objective is to assess the safety and tolerability of PDA10
3. The aim of the open-label extension phase is to assess the long-term safety and tolerability of PDA10

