10.4.4. Selection of Dosages in the Study

1) Observation period

In order to evaluate the Hb level of patients for screening, patients will be monitored on the Eprex[®] dosage previously treated for four weeks from screening visit and the Hb levels will be monitored every 2 weeks. When the Hb level and iron status meet the following criteria, the patients will proceed to the maintenance phase or the titration phase.

- **Criteria to proceed the maintenance phase without titration phase**

Patients on Eprex[®] treatment for at least 12 weeks and with hemoglobin within the target range of 10.0 to 12.0 g/dl and a stable IV dose of Eprex[®], and adequate iron store (serum ferritin level \geq 100 ng/mL and/or transferrin saturation \geq 20%) during observation period will proceed to enter the maintenance phase. Hb level measured during this observation period will be considered as baseline level.

- **Criteria to proceed the titration phase**

- 1) Patients treated with other EPO products for at least 12 weeks

If the patients are treated with other EPO products, the patients should proceed to the titration phase to exposure the Eprex[®] for at least 12 weeks.

- 2) Hb is below 10 g/dL even if the patients were treated with Eprex[®] for at least 12 weeks; in the event a patients' Hb is to decline below 10 during the observation period, patients should switch to titration phase.

2) Titration phase

The initial dosage of Eprex[®] will be the same with the erythropoietin dosage previously treated. However, the increased dosage will be treated for the initial dosage if Hb level is less than 10 g/dl prior to Screening Visit. The Hb level of patients is monitored every 2 weeks during titration phase. Eprex[®] dose changes will be made every four weeks on the basis of the most current Hb level—more frequent changes will be made only when the Hb value or the rate of Hb change is outside the preset safety as follows;

- If Hb level increase in the past two weeks is > 1.0 g/dL or Hb level is approaching 12 g/dL, the dose will be decreased by 25% of current dosage. If the hemoglobin continues to increase or exceed 12 g/dl, the treatment should be temporarily withheld until the hemoglobin begins to decrease, at which point therapy should be reinitiated at a dose approximately 25% below the previous dose. If dose reduction is needed, the amount given per dose or the number of weekly injections will be reduced, or both will be reduced.

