10.4.5. Blinding

All PFSs will have the same external appearance and composition.

A list of subjects randomization codes will be generated by LSK global PS (an electronic version will be stored in a secure locked area). The list of patient randomization codes will be generated using PROC PLAN in the SAS[®] procedures. A stratified block randomization approach will be used for the randomization with stratification factor of country and study site. This list will identify each patient by randomization number and include the patient's corresponding treatment assignment. The randomization codes will be provided in a secure manner to the IWRS developer and the study drug packaging provider.

When the maintenance of the safety and well-being of the patient, as assessed by the Investigator, requires that the administered study treatment be revealed, the Investigator shall break the blind. Before a study drug is unblinded, every attempt should be made to discuss the case with the Sponsor to evaluate whether or not to break the blind. Unblinding will be done through the IWRS system. Accessing the IWRS for emergency unblinding should be done only in an emergency that necessitates identifying the study drug for the welfare of the patient.

An explanation for breaking the blind will be recorded in the relevant source documents. Breaking the code at the investigative study center will immediately disqualify the patient from further participation in the study.

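### The primary ANCOVA is valid but leaves out entry route and the other co-primary's baseline, which are known before randomization; adding them is a free, modest gain in precision

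*Protocol*

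**What the plan says.** Protocol section 10.6.4.1, repeated under Statistical methods in the synopsis, specifies the primary model: "The intervals will be calculated by means of ANCOVA model including treatment group as a factor and study center and baseline value as covariates". Baseline value is in the singular and is most naturally the endpoint's own baseline. The same section says that hemoglobin and epoetin dosage for the baseline period are both collected at Weeks -4, -2 and 0.

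Section 10.4.4 sets out two ways to reach randomization.

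- **Direct entry**, under "Criteria to proceed the maintenance phase without titration phase": at least 12 weeks on Eprex, hemoglobin 10-12 g/dl, a stable dose and adequate iron during the observation period.
- **Titration**, for two kinds of patient. One is "Patients treated with other EPO products for at least 12 weeks". The other had hemoglobin below 10 g/dl despite at least 12 weeks on Eprex. Section 10.1 gives titration 12 weeks, extendable to 20.

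Section 10.4.5 on randomization: "A stratified block randomization approach will be used for the randomization with stratification factor of country and study site". Route is not a stratum. Section 6 on the number of sites: "This study will be performed at approximately 20 study centers located in Korea and Malaysia".

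**The concern.** Equivalence is decided by where the interval lies and how wide it is. A pre-randomization variable that predicts the change to Weeks 24-28 and is left out of the model stays in the residual variance and widens the interval. Route is a plausible predictor. Adjusting for a patient's baseline level does not record how recently that level was reached, or whether the patient came from another product. Baseline dose is a plausible predictor of hemoglobin change, and baseline hemoglobin of dose change, since section 10.6.4.1 itself describes dosage and hemoglobin as closely linked. All of these data are in hand before the first randomized dose, so leaving them out saves nothing.

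**Working it through.** **Inputs from the protocol.** Section 10.6.7.2: SD of change 1.1 g/dl (hemoglobin) and 86.6 IU/kg (weekly dose), margins 0.5 and 45, true difference 0, 1:1 allocation. Section 10.6.7.1: 126 evaluable per group.

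**The plan's own figure.** n = 2 × (1.645 + 1.96)² × SD² / margin².
- Hemoglobin: 2 × 3.605² × 1.1² / 0.5² = 125.80, so 126.
- Dose: 2 × 3.605² × 86.6² / 45² = 96.26, so 97.

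Both reproduce. This sum of z-values arises with alpha 0.05 per side and 95% power, or with alpha 0.025 per side and 90% power, so power is shown both ways below.

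**Precision.** Half-width = 1.645 × SD × √(2/126) × √(1 − R²). R² is the share of residual variance that the added terms explain. The documents give no value, so it is an assumed range. The planning SDs are taken as the residual SDs of the current model.

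| R² (assumed) | Half-width, Hb (g/dl) | Half-width, dose (IU/kg/week) | n per group for same Hb power | Hb power, 0.05 per side | Hb power, 0.025 per side | Dose power, 0.05 per side |
|---|---|---|---|---|---|---|
| 0 | 0.228 | 17.9 | 126 | 95.0% | 90.1% | 98.7% |
| 0.05 | 0.222 | 17.5 | 120 | 96.0% | 91.8% | 99.0% |
| 0.10 | 0.216 | 17.0 | 114 | 96.9% | 93.5% | 99.3% |

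**What route alone could contribute.** If a share p is titrated and the routes differ by D in mean hemoglobin change, route explains p(1 − p)D²/SD². With p = 0.5:
- D = 0.25 g/dl: 0.25 × 0.0625 / 1.21 = 1.3%
- D = 0.5 g/dl: 0.25 × 0.25 / 1.21 = 5.2%
- D = 1.0 g/dl: 0.25 × 1 / 1.21 = 20.7%

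Both p and D are assumptions. Route reaches the 5-10% range on its own only if D is about 0.5 g/dl or more.

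**Chance imbalance in route.** The SD of the between-arm difference in titrated share is √(2p(1 − p)/126). This is 0.063 at p = 0.5 and 0.050 at p = 0.2, so the 95% range is about ±12 and ±10 percentage points. With D = 0.5 g/dl the estimate could move by up to 0.062 and 0.049 g/dl, or 12% and 10% of the margin.

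This movement is already in the standard error. At p = 0.5 and D = 0.5, the variance of the shift is (0.063 × 0.5)² = 0.00099. The variance of the treatment difference is 1.1² × 2/126 = 0.0192. The ratio is 5.2%, exactly the R² above. Adjustment removes that 5.2%; without adjustment the interval carries it.

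**Validity check.** A simulation used 252 patients, 20 centers, half on each route, an assumed between-center SD of 0.3 and 3,000 runs. Ranges are over route effects of 0, 0.5 and 1.0 g/dl.

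| Model | Type I error at the margin | Power at 0 / 0.5 / 1.0 g/dl |
|---|---|---|
| Center as one linear term | 0.042-0.046 | 94.9 / 95.5 / 96.4% |
| Center categorical | 0.047-0.051 | 95.6 / 95.7 / 96.4% |
| Center categorical plus route | 0.045-0.049 | 95.6 / 96.3 / 98.9% |

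The simulation error of a type I rate is about √(0.05 × 0.95/3000) = 0.004, so no model exceeds 5% beyond noise.

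**Degrees of freedom.** Spending 19 degrees of freedom on about 20 centers moves the t quantile only from 1.6510 (249 df) to 1.6515 (230 df).

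**The case against.** The strongest reply is that this is a refinement and not an error. Adjusting for center and baseline is a sound analysis of a randomized comparison, and further covariates are often settled in the statistical analysis plan, which is not at hand. That stands as to validity. It does not remove the point, because the protocol writes out the primary model in full in two places.

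A reader might infer more than the documents support in four ways.

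- **That the routes are two very different populations.** Sections 10.3.1 and 10.4.4 hold both to hemoglobin 10-12 g/dl on a stable dose over the four weeks before randomization. Titrated patients have also been on Eprex for about 12 weeks or more by then. No figure in the protocol shows that route predicts later change.
- **That center would be fitted as a slope on a site number.** The text calls center a covariate but never calls it numeric. This is loose wording. Even on the literal reading, the simulated type I error did not exceed 5%.
- **That the objective requires baseline dose in the hemoglobin model.** Section 8 asks for equivalence "in the change in hemoglobin from baseline, while taking into account differences in epoetin dosage". That concerns dosage differences between arms. The protocol meets it by making dose co-primary (section 10.2) and requiring both levels of the hierarchy to succeed.
- **That imbalance in route biases the result.** As shown above, it is part of the stated uncertainty. The primary analysis uses the per-protocol population, with 20% exclusion assumed, and randomization does not strictly guarantee balance in that subset. But nothing in the protocol links exclusion to route, and a route term would be only a partial safeguard.

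**Conclusion.** The point holds as a free precision improvement. The planned model is valid. It simply does not use entry route or the second baseline, both known before randomization, and nothing in the design balances route. On an assumed 5-10% of residual variance explained, the half-widths narrow by 2.5-5.1% (1 − √0.95 and 1 − √0.90), worth 6 to 12 patients per group (126 against 120 and 114). If the true share is nearer 1-2%, the gain is negligible; it becomes substantial only near 20%, where required n falls to 101. The documents cannot say which applies. The case for the change is that it costs almost nothing, not that the trial is at risk without it.

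**What to change.** In section 10.6.4.1 and in the synopsis, state the model for both co-primary endpoints as ANCOVA with treatment, study center (categorical, as randomized) and entry route (direct or titrated) as factors, and baseline hemoglobin and baseline weekly dose per kg as continuous covariates. Define route as whether the patient entered the titration phase before randomization, so that a patient moved from observation to titration counts as titrated. Keep the current model as a sensitivity analysis, and make the change before unblinding.

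In the same edit, align the baseline definitions. Section 10.6.4.1 mentions only the last four weeks of titration, whereas the synopsis also allows the observation period, which direct entrants need in order to have a baseline.

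The cost is one sentence in two places and no new data. It uses two degrees of freedom if center is already categorical. If center was meant as a single term, about 18 more are used, with negligible effect on the interval.

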10.6.4.2. Secondary Efficacy Variables

Summaries of categorical variables (nominal or ordinal) will include frequency and percentage of patients at each level of response. Continuous variable summaries will include n, mean, median, standard deviation, minimum and maximum values.

Treatment difference will be analyzed using two sample t-test or Wilcoxon rank-sum test for continuous parameters, and using χ^2 -test or Fisher's exact test for categorical parameters.

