Methodology	
This study is a multi-center, multi-national, randomized, double-blind, active-controlled and parallel group clinical trial. Eligible subjects will be randomized, using IWRS, to receive one of the two study treatment regimen (PDA10 or Eprex[®]) in a 1:1 ratio. All subjects are to continue their treatment PDA10 or Eprex[®], and to receive study medication 1-3 times weekly intravenously (refer to Appendix III).
 
During 12-week of the titration phase, all subjects will receive Eprex[®], then

CLINICAL STUDY SYNOPSIS: Study PG-EPO-Ph3	
	
those with hemoglobin within the target range of 10.0 to 12.0 g/dl and a stable IV dose (a dosage titrated and individualized) of Eprex[®] at baseline period will be randomly assigned to one of two study drugs, either to the test product, PDA10, or to the reference product, Eprex[®]. During the maintenance phase, the efficacy and safety of two groups will be evaluated every 2 weeks or 4 weeks.
 
Subjects who complete the maintenance phase will be offered the choice of participating 24-week open-label extension phase. During the open -label extension phase, PDA10 will be administered and the long-term safety will be evaluated.

Primary endpoint(s):	
 • Mean change in hemoglobin level between the baseline period and the evaluation period • Mean change in weekly dosage per kg body weight between the baseline period and the evaluation period 
* The baseline period is the last four weeks of titration phase or the observation period and the evaluation period is the last four weeks of maintenance phase. Hemoglobin, hematocrit and the dosage of epoetin for the baseline period will be collected at Week -4, Week -2 and Week 0, and those for the evaluation period will be collected at Week 24, Week 26 and Week 28.

Secondary endpoint(s):	
 • Mean change in hematocrit levels between the baseline period and the evaluation period • Proportion of patients with hemoglobin level out of the target range during the maintenance phase • Proportion of patients with hemoglobin level within the target range during the evaluation period • Frequency of patients with changes in the dosage per kg body weight • Incidence of blood transfusions
Safety endpoint(s):	
 1) Adverse Events 2) Occurrence of anti-epoetin antibodies 3) Vital Signs 4) Physical Examination 5) Clinical Laboratory Determinations

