10.6. STATISTICAL METHODS

10.6.1. General Principles of the Result Analysis

Statistical analyses will be performed using the data analysis software SAS® Version 9.2 or higher.

Statistical testing will be done at alpha=0.05 level, two-sided, without any adjustment for multiple comparisons unless otherwise specified. The p-values will be rounded to 4 decimal places; p-values less than 0.0001 will be presented as “<.0001” in all tables.

Summaries of categorical variables (nominal or ordinal) will include frequency and percentage of patients at each level of response. Continuous variable summaries will include n, mean, median, standard deviation, minimum and maximum values.

The primary efficacy analysis will be based on the PP population.

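### Secondary efficacy endpoints get unadjusted tests of difference and no stated interval; adjusted estimates with confidence intervals would be a minor improvement at no cost

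*Protocol*

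**What the plan says.** Section 10.6.4.2 covers the secondary efficacy endpoints in two steps. The first is descriptive: "Continuous variable summaries will include n, mean, median, standard deviation, minimum and maximum values", with frequencies and percentages for categorical variables. The second is a comparison: "Treatment difference will be analyzed using two sample t-test or Wilcoxon rank-sum test for continuous parameters", and chi-square or Fisher's "exact test for categorical parameters". The synopsis repeats this. By the default in section 10.6.1, "Statistical testing will be done at alpha=0.05 level, two-sided, without any adjustment for multiple comparisons unless otherwise specified".

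Neither place names a covariate, a centre or country term, or an interval for the treatment difference.

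Two other parts of the protocol bear on this:

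- Section 10.4.5, on allocation: "A stratified block randomization approach will be used for the randomization with stratification factor of country and study site".
- Section 10.6.4.1, on the two primary endpoints: "The intervals will be calculated by means of ANCOVA model including treatment group as a factor and study center and baseline value as covariates".

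The synopsis lists five secondary endpoints. One is clearly continuous: "Mean change in hematocrit levels between the baseline period and the evaluation period". The other four are proportions or frequencies: hemoglobin outside target during maintenance, hemoglobin within target during evaluation, patients with dose changes, and transfusions.

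**The concern.** Hematocrit change is built like the primary hemoglobin change. Section 10.6.4.1 collects both at Weeks -4, -2 and 0 and again at Weeks 24, 26 and 28. Hemoglobin is then analysed with centre and baseline in the model and hematocrit without either, so two closely linked measurements are estimated in different ways for no stated reason. The proportion endpoints are compared without the factors used to balance the allocation.

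The form of the result matters more than the model. The trial aims to show equivalence, and the primary endpoints are properly judged by intervals. For the secondary endpoints the protocol provides only a test of no difference. Such a test does not show which differences remain compatible with the data, and that is what a reader of an equivalence trial needs from supportive endpoints.

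**Working it through.** **Group size.** Section 10.6.7.2 gives 2 × (1.645 + 1.96)² × 1.1² / 0.5² = 125.80, rounded up to 126 per group. With 20% excluded from the per-protocol set, 126 / 0.8 = 157.5, rounded up to 158 per group and 316 in total. Both figures reproduce. The protocol states no figure for any secondary endpoint, so 126 per group is used below only as the evaluable size.

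**What a test of difference can say at this size.** For a continuous endpoint in SD units, SE = √(2/126) = 0.126. Two-sided 5% power is about Φ(effect/0.126 − 1.96).

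- 0.2 SD: 35%
- 0.3 SD: 66%
- 0.4545 SD (the hemoglobin margin in SD units, 0.5/1.1): 95%

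The 95% interval half-width would be 1.96 × 0.126 = 0.247 SD. For a 10-point difference in a proportion, with an assumed reference rate of 50% to 90%, power is 36% to 61%. The 95% half-width at those rates is 12.3 to 7.4 points.

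**Ignoring the strata.** When allocation is balanced within centre, centre differences cancel from the treatment contrast but stay in the SE of the unadjusted test. That SE is too large by 1/√(1 − ICC). A simulation of the t-test used 20 centres of 12 patients, balanced 1:1 within centre, with 20,000 runs. The ICC values are assumptions, since the protocol gives none.

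| Assumed centre ICC | SE overstated by | Actual type I error at nominal 5% |
|---|---|---|
| 0.05 | about 3% | 4.5% |
| 0.10 | about 5% | 3.8% |
| 0.20 | about 12% | 2.9% |

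**Adding baseline as a covariate (hematocrit).** Let s0 and s1 be the baseline and evaluation SDs and ρ their correlation. Then

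- Var(change) = s0² + s1² − 2ρ·s0·s1
- residual variance in ANCOVA = s1²(1 − ρ²)

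If s0 = s1, the ratio is (1 + ρ)/2. At ρ = 0.2, 0.5 and 0.7 it is 0.60, 0.75 and 0.85, with square roots 0.775, 0.866 and 0.922. Intervals would be 23%, 13% and 8% narrower.

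Equal variances are doubtful here. Section 10.3.1 requires hemoglobin of 10-12 g/dl during the baseline period, while evaluation values may leave that range. A uniform spread over 10-12 has SD 2/√12 = 0.58. Take s0 = 0.58 and the protocol's change SD of 1.1, and assume that hematocrit behaves as scaled hemoglobin. Solving the first formula for s1 gives:

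| ρ (assumed) | s1 | Variance ratio | Interval narrower by |
|---|---|---|---|
| 0.2 | 1.06 | 0.89 | 5.7% |
| 0.35 | 1.16 | 0.98 | 1.2% |
| 0.5 | 1.27 | 1.00 | 0.1% |

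At ρ = 0.7 the gain would be 7.6%, but the implied regression slope of evaluation on baseline is 0.7 × 1.42 / 0.58 = 1.7, which is implausible. The range that fits the entry rule is therefore about 0-6%.

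**Choice of strata for the proportions.** 252 patients over about 20 centres (section 6) is 252/20 = 12.6 per centre, or about 6 per group. Such strata are sparse for uncommon events. The trial has only two countries, Korea and Malaysia.

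**The case against.** The strongest reply is that nothing here is wrong. Under randomisation the change-score t-test and the ANCOVA are both valid for the same contrast, and ignoring the strata does not inflate type I error. Baseline already enters hematocrit through the change score, and its use as a covariate has little bearing on the four categorical endpoints. The secondary endpoints carry no margin. Section 10.6.4.1 rests the equivalence claim on the two primary endpoints alone. Displaying an interval beside a test, or giving the rule for choosing t-test or Wilcoxon, is commonly left to a statistical analysis plan, and this trial may have one. All of this stands, and it limits the point to an improvement. What remains is that the protocol itself names the tests, and better ones are available from data it already collects.

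A reader might infer that the sponsor means to treat a non-significant secondary p-value as evidence of similarity. No section says so. The point is only that a test of difference carries little information for an equivalence question. The test is also not weak at every scale: against a difference as large as the hemoglobin margin in SD units it has 95% power.

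A reader might also take 8-23% as the precision lost. That needs equal variances at baseline and evaluation, which the entry rule makes doubtful.

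Finally, stratifying the proportions by country recovers only part of what site stratification put into the design. That is true, and it is the price of avoiding sparse strata.

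**Conclusion.** The point holds as a minor improvement at no cost. Section 10.6.4.2 fixes unadjusted tests and states no interval for the treatment difference, although the trial stratifies its randomisation and already adjusts its primary model. The tests are valid and mildly conservative, by an amount that rests on the assumed ICC of 0.05 to 0.20. The main gain is the interval: power of 35% at 0.2 SD shows how little a p-value above 0.05 would exclude. The gain from the baseline covariate is about 0-6% under the restricted baseline spread assumed above and reaches 8-23% only with equal variances. The documents give neither the correlation nor the hematocrit variances. The sample size, the alpha for the primary tests and the primary equivalence conclusion are not affected.

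**What to change.** In section 10.6.4.2 and the matching synopsis text:

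- Analyse hematocrit change with the same ANCOVA as the primary endpoints (treatment, centre, baseline value) and report the adjusted difference with its confidence interval. This replaces the open choice between t-test and Wilcoxon.
- For the proportion endpoints, report the risk difference with a 95% confidence interval, stratified by country (Mantel-Haenszel). Keep an exact method where events are few, as transfusions may be.
- State that these results are supportive and that a non-significant p-value is not evidence of equivalence.

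The cost is wording in two places. No new data, visits or patients are needed.
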